5.2 PARTICIPANT DISPOSITION

Descriptive statistics will be used to summarize study conduct measures for the all enrolled population, such as study disposition (including premature withdrawals from treatment), incidence of protocol deviations, percentage of intended dose administered, and incidence of incorrect treatment allocation.

All protocol deviations will be listed. Furthermore, the protocol deviations related to epidemic/pandemic will be listed separately.

5.3 DEMOGRAPHIC DATA AND BASELINE CHARACTERISTICS

Baseline characteristics will be analyzed descriptively for the SE population by previous randomization and by actually received up-titration scheme and overall. The patients' demographics and DB screening or OLE baseline variables include, but are not limited to the following:

- Sex
- Age at DB screening
- Age at OLE baseline
- Race

- Years of education
- Weight
- Height
- Body mass index
- Region
- APOE ϵ 4 carrier status (yes vs no)
- APOE genotype (0 ϵ 4, 1 ϵ 4, or 2 ϵ 4)
- ARIA-E during DB period (yes vs no)
- Cumulative ARIA-H at OLE baseline
- MMSE total score at OLE baseline
- ADAS-cog (13-items score) at OLE baseline
- ADCS-ADL at OLE baseline
- Clinical Dementia Rating – Sum of Boxes (CDR-SB) at OLE baseline
- Clinical Dementia Rating - Global score at OLE baseline

5.4 PREVIOUS AND CONCOMITANT MEDICATION AND MEDICAL HISTORY

The medical history, previous medication and concomitant medication data will be coded using the WHO Drug Dictionary version that is current at the time of the analysis (WHO Drug 1 March, 2021), and will be summarized for the SE populations by previous randomization and overall:

- Medical history is defined as a record of all medical events (for example: procedures and diseases) of a patient that started prior to the date of the first dose of study treatment in the DB part.
- Previous medication is defined as all received medications of a patient that ended prior to the date of the first dose of study treatment in the DB part.
- Concomitant medications are classified into the following four categories.
 - Medications ongoing at first dose in the DB is defined as all received medications of a patient that started prior to and were still ongoing on the date of the first dose of study treatment in the DB part.
 - Medications used after first dose in the DB is defined as all received medications of a patient used after the first dose of study treatment in the DB part.
 - Medications ongoing at first dose in the OLE is defined as all received medications of a patient that were still ongoing on the date of the first dose of study treatment in the OLE.
 - Medications used after first dose in the OLE is defined as all received medications of a patient that started after the date of the first dose of study treatment in the OLE.

If the medical event (for example: treatment, procedure or disease) does not have complete or valid start and end dates, the following rules will be applied. The reference date is defined as the date of the first dose of study treatment.

If the medical event start date is (a) completely missing, or (b) only has the year specified, and this is the same as the year of the reference date, or (c) only has the month/year specified, and these are the same as the month/year of the reference date, then the medical event will be assumed to have started before the reference date.

If the medical event end date is (a) completely missing, or (b) only has the year specified, and this is the same as the year of the reference date, or (c) only has the month/ year specified, and these are the same as the month/ year of the reference date, then the medical event will be assumed to have ended after the reference date.

Otherwise, partial medical event start and end dates (month/year or year only) will be compared with the corresponding part of the reference date to determine whether strictly before or strictly after the reference date (no other possibility exists, because this is covered by the two previous points).

5.5 EFFICACY ANALYSES

Efficacy outcomes of CDR, MMSE, ADAS-Cog13, ADCS-ADL at OLE baseline, OLE Week 52/104 were assessed and collected in the initial two years of the OLE, while only MMSE was assessed and collected every 6 months thereafter. The rating scale ADAS-Cog, ADCS-ADL, CDR and MMSE were captured electronically and transferred to the database directly from the core laboratory. During the OLE additional years, the MMSE was performed as a paper-and-pencil scale and recorded on the eCRF form. Definition and schedules of these measurements can also be found in the Section 4.5.5 and Appendix 2 of the study protocol.

For each of these outcome measures, the total scores and change from the OLE baseline will be summarized by previous randomization and overall at each visit. All efficacy analyses will be descriptive.

5.5.1 Alzheimer Disease Assessment Scale-Cognition

The modified ADAS-Cog with a 13-item total score was used in the study. The 13-item total score is calculated using the sum of all the 13-item scores.

If any item score is missing or is invalid, the total score will be set to missing. The 13-item ADAS-Cog total score has a range of 0–85. Higher scores indicate greater impairment.

5.5.2 Mini Mental State Exam

The MMSE comprises 11 items to assess a participant's mental status and identifies the individual's general level of impairment in five areas: orientation, short-term memory

retention, attention, short-term recall, and language. The total score is calculated by summing the scores of all 11-items; the maximum total score is 30.

If any item score is missing or invalid, the item score will be set to 0. The total score ranges from 0 to 30 with lower values indicating greater impairment.

5.5.3 Clinical Dementia Rating Scale–Global Score

The CDR global score is calculated based on Washington University’s CDR assignment algorithm (<https://biostat.wustl.edu/~adrc/cdrpgm/index.html>). Investigators enter scores from each of the six categories (“box scores”), and the CDR global score is calculated using a calculator available at <http://www.biostat.wustl.edu/~adrc/cdrpgm/index.html>.

The global CDR score is derived from the scores in each of the six categories (“box scores”) and is determined as follows (Memory [M] is considered the primary category, and all others are secondary):

- CDR = M if at least three secondary categories give the same scores as memory.
- CDR = score of majority of secondary categories with at least three secondary categories given a score greater or less than the memory score on one side of M, except in the case of CDR = M (see the subsequent point).
- CDR = M when three secondary categories are scored on one side of M and two secondary categories are scored on the other side of M.
- If M = 0.5, then CDR cannot be 0 and it can only be 0.5 or 1; CDR = 1 if at least three of the other categories are scored ≥ 1 .
- If M = 0, then CDR = 0; if there are impairments (≥ 0.5) in two or more secondary categories, then CDR = 0.5.
- When there are ties in the secondary categories on one side of M, the chosen tied score for CDR is the closest score to M (e.g., If M and another secondary category = 3, two secondary categories = 2, and two secondary categories = 1, then CDR = 2).
- When only one or two secondary categories are given the same score as M, then CDR = M as long as no more than two secondary categories are on either side of M.
- When M ≥ 1 , then CDR cannot be 0; in such a circumstance, CDR = 0.5 when the majority of secondary categories are 0.

5.5.4 Clinical Dementia Rating – Sum of Boxes

The CDR-SB score is obtained by summing each of the domain box scores. Thus, the CDR-SB score for a patient ranges from 0 to 18 with a higher score indicating greater impairment. The electronic administration of this scale does not allow missing data.

5.5.5 Alzheimer’s Disease Cooperative Study – Activities of Daily Living

The ADCS-ADL is the scale most widely used to assess functional outcome in patients with AD. The ADCS-ADL consists of 32 items (questions and sub-questions) each with multiple choice answers. For example, questions with three possible responses often have the following response structure (3 points = without supervision or help, 2 points = with supervision, 1 point = with physical help). Total score is calculated by summing all sub-scores. The ADCS-ADL total score ranges from 0–78 with lower values indicating greater impairment.

This scale is administered electronically with no option to miss a question. Therefore, missing data will only be present if the entire scale is missing. However, due to a translation error in Spanish for Spain, Question 18 will be set to missing for all patients from Spain. Total scores will be missing for these patients.

5.6 PHARMACOKINETIC AND PHARMACODYNAMIC ANALYSES

5.6.1 Pharmacokinetic and Anti-Drug Antibody Analysis

Plasma concentration data for gantenerumab will be descriptively summarized by nominal time/visit including, but not limited to the arithmetic mean, median, standard deviation and range.

A population PK model previously developed using nonlinear mixed-effects modeling (1105289) will be used to derive individual measures of exposure including C_{max} , C_{min} , and AUC_T at steady state. These parameters will be descriptively summarized including, but not limited to, arithmetic mean, median, standard deviation, range, and coefficient of variation.

Data on anti-drug antibodies (ADAs) will be summarized from the first dose of gantenerumab to the start of OLE and from the start of OLE to the end of study. Furthermore, their effect on gantenerumab plasma PK will be assessed graphically, as appropriate.

5.6.2 Pharmacodynamic and Exploratory Biomarker Analysis

The PET substudy (WN28745-PET) was initiated in the double-blind period. Florbetapir¹⁸F (Amyvid TM) was the tracer used for all patients in this substudy. Brain amyloid imaging was considered a pharmacodynamic (PD) measurement of potential effects of gantenerumab on amyloid load in the brains of patients with mild AD. There were up to 4 assessments included in the analysis: OLE Baseline, OLE Week 52, OLE Week 104 and OLE Week 156. Note that the OLE baseline measurement should occur within 9 months prior to the start of OLE. All patients participating in the DB part of the PET substudy (approximately 100 patients in the WN28745 PET substudy) were invited to continue in the OLE part to assess changes of brain amyloid load over time with gantenerumab treatment. No patients started the PET substudy in the OLE.

A prespecified standard uptake value ratio (SUVR) method, identical to the method report for analyses from the DB part of the study, was used. SUVR values were also converted to centiloid values to provide a more intuitive interpretation of amyloid reduction. Centiloid zero is the mean amyloid burden for a typical population of young healthy controls, 100 centiloid is the typical mean of a population with AD, and 24 centiloid is consistent with the diagnostic amyloid positivity threshold (Klunk et al. 2015; Navitsky et al. 2018).

The equation for conversion of florbetapir SUVR to centiloid is specified using the mean cerebellar gray reference region (Klein et al. 2019):

$${}^{\text{FBP}}\text{CL} = 184.118 \times {}^{\text{FBP}}\text{SUVR} - 233.718$$

${}^{\text{FBP}}\text{CL}$ = florbetapir centiloid; ${}^{\text{FBP}}\text{SUVR}$ = florbetapir standard uptake value ratio.

For the SUVR and Centiloid measures, the value and change from the OLE baseline will be summarized by visit and by previous randomization, and overall. A mixed model for repeated measurement (MMRM) may also be used if applicable.

5.6.3 Magnetic Resonance Imaging Volumetric Measures

The ventricular volume and the percentage change from the DB screening in hippocampal volume, whole brain volume and cortical grey matter volume were assessed at OLE Week 52, OLE Week 104 and OLE Week 152. These volumetric measures will be summarized by previous randomization and overall using descriptive statistics and analyzed by mixed model of repeated measurement if applicable.

- Ventricular volume is a validated automated measurement of the volume of the lateral ventricles. The method is based on anatomic non-linear image matching and labeling with a minimum deformation template library (Fonov et al. 2010, 2011) and local patch-based label fusion (Coupe et al. 2011).
- The percentage change in hippocampal volume measurement relies on a locally developed longitudinal image-processing pipeline that builds a subject-specific MRI average template using all available time points.
- The percentage change in whole brain volume is measured based on Jacobian integration using locally developed JacobianAtrophy software (Nakamura et al. 2013). A T1w image with the same image acquisition parameters must exist for the two timepoints over which the percent whole brain volume change is to be calculated.
- The percentage change in cortical grey matter volume is calculated within the cortical grey matter volume mask using the JacobianAtrophy software described above for the percent brain volume change

See the MRI charter for details of the MRI volumetric measures.

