1.1 OBJECTIVES AND OUTCOME MEASURES

1.1.1 Objectives

The primary objective of the OLE was to evaluate the safety and tolerability of gantenerumab at doses up to 1200mg every 4 weeks, focusing on physical and neurologic examinations, vital signs, blood safety tests, ECGs, and adverse event (AE) monitoring.

The secondary objectives included the following:

- To evaluate the effect of higher doses of gantenerumab on imaging biomarkers (positron emission tomography [PET] and magnetic resonance imaging [MRI]), cerebrospinal fluid (CSF) biomarkers, and on clinical outcome measures (cognition and function) over time
- To explore gantenerumab pharmacokinetics (PK) at higher doses.

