1.1.2.2 Biomarker Outcome Measures

The biomarker outcome measures for this study were as follows:

- Change from baseline (DB screening visit) to OLE Week 104 in MRI volumetry, as assessed on structural MRI:
 - Change from baseline in hippocampal volume
 - Change from baseline in whole brain volume
 - Change from baseline in cortical thickness
 - Change from baseline in ventricular volume

Change from baseline (DB screening visit) to OLE Week 104 in functional brain connectivity, as measured by resting state-MRI, was an exploratory biomarker outcome measure, and its analysis will not be covered in this SAP.

- Change in brain amyloid load over time using a florbetapir F18 injection, a PET radioligand selective to β -amyloid
- The analysis of the CSF biomarker will not be covered in this SAP.

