5. STATISTICAL ANALYSES

5.1 GENERAL CONSIDERATION

In the following sections, for all continuous variables for which descriptive statistics are indicated, the following statistics will be reported: the number of observations, the mean, median, standard deviation, and minimum and maximum. The 25th and 75th percentiles (Q1 and Q3) will also be reported for selected tables.

Statistical analyses will primarily focus on safety aspects in the OLE. The efficacy analyses, including clinical/cognitive measures, will be descriptive and strictly exploratory in nature:

- The start of OLE is defined as the date when patients received the first dose of gantenerumab in the OLE.
- The OLE baseline is defined as the last available assessment up to and including the first day of study drug intake in the OLE. Thus, the OLE baseline could be in the DB part.
- The end of the study is defined as the date of the last visit (including the last scheduled follow-up visit according to the study protocol) of the last participant in the study.

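### In the OLE, volume change on MRI is measured only from double-blind screening for three of four measures, so the OLE Week 52 figure mixes 13 to 112 weeks of pre-OLE time with the higher-dose period.

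*SAP*

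**What the plan says.** The OLE SAP lists a secondary objective "To evaluate the effect of higher doses of gantenerumab on imaging biomarkers", with MRI among them (1.1.1). For volumetry, 1.1.2.2 sets the measure as "Change from baseline (DB screening visit) to OLE Week 104 in MRI volumetry, as assessed on structural MRI". Section 5.6.3 then gives "percentage change from the DB screening in hippocampal volume", and the same for whole brain and cortical grey matter volume, assessed at "OLE Week 52, OLE Week 104 and OLE Week 152". These are summarised by previous randomization and overall and "analyzed by mixed model of repeated measurement if applicable". Ventricular volume differs: 5.6.3 lists it as a volume, while 1.1.2.2 lists it as a change from double-blind (DB) screening.

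The same SAP defines another anchor: "The OLE baseline is defined as the last available assessment up to and including the first day of study drug intake in the OLE" (5.1). It uses that anchor for the clinical scales (5.5) and for PET, where "the value and change from the OLE baseline will be summarized by visit and by previous randomization, and overall" (5.6.2). It gives no reason for treating volumetry differently, and it names no within-OLE contrast and no covariate for elapsed time.

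**The concern.** Patients entered the OLE at different points of the DB part. Entry depended on approval of the amendment in each country (Part 1 SAP, section 2), and many patients had not reached Week 104 (Part 1 SAP 2.2). A change measured from DB screening to a fixed OLE week therefore adds a common OLE period to a pre-OLE period whose length varies by patient.

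Two things are at stake. First, a mean at OLE Week 52 depends partly on how long patients had been in the DB part, and the overall column averages unlike durations. Second, splitting by previous randomization does not repair this. The pre-OLE time was on placebo in one group and on 105 or 225 mg in the other, so a difference between the groups carries DB treatment into a result labelled OLE.

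**Working it through.** The documents state no elapsed interval, so there is no figure of theirs to reproduce. The interval follows from their dates and visit schedule.

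**Inputs**
- Last DB randomization: 9 December 2015 (Part 1 SAP, section 1).
- OLE enrolment: 3 March 2016 to 31 July 2017 (OLE SAP, section 1).
- Screening lead, s: 1 to 8 weeks before Day 1 (protocol Appendix 1, Table 1).
- DB period: 100 weeks of treatment, final assessment at Week 104 (Part 1 SAP, section 2).

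**Step 1. Elapsed time at OLE Week 52.** T = s + d + 52, where d is weeks from DB Day 1 to the first OLE dose.
- Smallest d: 9 December 2015 to 3 March 2016 is 85 days, and 85/7 = 12.1 weeks.
- Minimum T: 1 + 12.1 + 52 = 65.1 weeks. With an 8-week lead: 8 + 12.1 + 52 = 72.1 weeks.
- Maximum T, assuming entry at DB Week 104: 8 + 104 + 52 = 164 weeks.
- 164 is not a hard ceiling. Entry at DB Week 116 would give 8 + 116 + 52 = 176, and Part 1 SAP 4.1.5 allows for gaps of more than 28 days before the first OLE dose.

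**Step 2. Share that precedes the OLE.**
- Minimum: 1 + 12.1 = 13.1 weeks, and 13/65 = 20%.
- Maximum: 8 + 104 = 112 weeks, and 112/164 = 68%.
- If atrophy were roughly linear and equally fast, two patients at these extremes would differ by 164/65 = 2.5-fold at the same labelled visit (164/72 = 2.3-fold with a common 8-week lead).

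**Step 3. What a Week 52 to Week 104 contrast does.** With volumes V0 at screening, V52 and V104:

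(V104/V0 − 1) − (V52/V0 − 1) = (V104 − V52)/V0

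The pre-OLE interval drops out and every patient contributes a nominal 52 weeks. By OLE SAP Table 1 all four schedules reach their last step by Week 24, so the contrast lies after scheduled titration. It says nothing about the first OLE year.

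**Step 4. What an OLE baseline would achieve.** DB volumetric scans were scheduled at screening, Weeks 24 and 48, and Week 104 or early termination (protocol Appendix 1). Appendix 2 schedules no MRI before OLE Day 1 or on that day. Using the last volumetric scan on or before OLE Day 1, the interval at OLE Week 52 is:

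| OLE entry at DB week | Last volumetric scan | Interval (weeks) |
|---|---|---|
| 12 to 24 | Screening | 1 + 12.1 + 52 = 65 to 8 + 24 + 52 = 84 |
| 24 to 48 | Week 24 | 52 to (48 − 24) + 52 = 76 |
| 48 to 104, no early-termination scan | Week 48 | 52 to (104 − 48) + 52 = 108 |

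The range falls from 65–164 to about 52–108 weeks. The spread is still 108/52 = 2.1-fold, and at the upper end 56/108 = 52% of the interval precedes the OLE.

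**The case against.** **The anchor may be deliberate.** Screening is the one pre-treatment volumetric scan scheduled for everyone, and it continues the baseline in protocol 3.5.2. PET was repeated before the OLE if the last scan was over 9 months old, and the clinical scales if over 6 months old (protocol Appendix 2 footnotes); volumetric MRI had no such rule. This stands as a reason to keep the screening-based summary. It does not justify having no other.

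**An OLE baseline only partly helps.** This stands: Step 4 shows no gain for entry before DB Week 24 and long intervals for some later entrants.

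**Little rests on the result.** The OLE SAP states no hypotheses (section 2) and focuses on safety, with efficacy exploratory (5.1). There is no concurrent control, so change from OLE baseline could not establish a higher-dose effect either. That limits the weight of the point. But PET and the clinical scales lack a control too and still use the OLE baseline.

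**Stronger readings to avoid**
- A reader might infer that the volumetric analysis can show nothing about the OLE period. It can: Step 3 removes the pre-OLE interval, and the optional MMRM could estimate that contrast. The SAP simply does not name it.
- A reader might infer that all volumetric results share the anchor. In 5.6.3 ventricular volume is a volume.
- A reader might take 65 and 164 weeks as observed, or as a range for one patient. They are extremes across different patients.
- A reader might assume that change from OLE baseline follows exactly from two screening-based percentages as (1+p2)/(1+p1)−1. Section 5.6.3 describes whole brain and cortical change as measured between two scans by Jacobian integration. Nothing in the documents shows that chaining such measurements equals a direct one.

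**Conclusion.** The point holds in this limited form. For hippocampal, whole brain and cortical grey matter volume, the planned OLE Week 52 change can cover about 65 to 164 weeks (72 to 164 with a common 8-week lead), with 13 to 112 weeks before the first OLE dose. It does not by itself isolate the higher-dose period, and the first OLE year stays mixed with DB time on placebo or 105/225 mg.

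The figures assume OLE entry between the earliest possible date and DB Week 104. The 2.5-fold comparison also assumes roughly linear atrophy at equal rates. The distribution of DB time at entry is not given, so neither the typical mix nor the effect on the SD can be sized. For an exploratory secondary objective this is a worthwhile improvement to the SAP, not a defect that undermines the study.

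**What to change.** Change OLE SAP 5.6.3 as follows:

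1. Keep the change from DB screening, labelled as the cumulative view.
2. Prespecify the within-patient OLE Week 52 to Week 104 contrast. A Week 104 to 152 contrast is less secure, because protocol Appendix 2, Table 5 flags volumetric measures at Week 104 but at no later visit.
3. Add change from the last volumetric scan on or before OLE Day 1 (DB Week 24, 48, or 104/early termination), annualised by actual scan dates. Report the gap from that scan to OLE Day 1, and the number of patients whose only pre-OLE volumetric scan is screening.
4. Measure that scan pair directly with the existing pipeline.
5. Include time from DB screening to OLE Day 1 in any MMRM.
6. State whether ventricular volume is reported as a volume or as a change, so that 1.1.2.2 and 5.6.3 agree.

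The cost is SAP wording and some extra processing of existing scans, with no added patient burden. Patients who entered before DB Week 24 gain nothing from item 3, intervals of up to about 108 weeks remain for some others, and annualising corrects for duration but still blends pre-OLE with OLE time.
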